5.3.4.4. Worst-Case Abnormality

The following worst-case post-baseline abnormalities L, N, or H will be determined per subject, per parameter, and for each analysis period, using all non-missing post-baseline records (including unscheduled and follow-up visits):

- L = low: at least one post-baseline result is classified as L.
- N = normal: all post-baseline results are classified as N.

– H = high: at least one post-baseline result is classified as H.

If, for a subject, both L and H are reported, the subject will be counted twice in the table: once with a worst-case L and once with a worst-case H.

5.3.4.5. Presentation of Results

No formal inferential statistics (p-values) will be derived.

Continuous parameters will be summarized by means of descriptive statistics (including 95% CI of the mean change) by parameter (and position if applicable), treatment group, and analysis window. Actual values and changes from baseline will be tabulated separately.

Boxplots of the actual values over time and of the mean (+- SE) change from baseline will be prepared for all parameters.

The analysis of abnormalities will focus on assessments reported during the treatment period. Results reported during the screening or follow-up period will only be listed.

Abnormalities of the actual values will be presented as shift tables of the worst-case abnormality versus the baseline abnormality. The table will be created per parameter (and position if applicable) and treatment group.

A frequency table of the number (percent) of subjects with treatment-emergent worst-case abnormalities per parameter and treatment group will be presented.

A listing per treatment group, per subject, and per time point of all post-baseline time points scored as treatment-emergent and out-of-normal-range, plus also the baseline reference time point will be provided.

The vital signs measurements collected at the start and finish of the 6MWT will be listed separately.

5.3.5. Physical Examinations

A listing per treatment group, per subject, and per time point of the selection of all abnormal findings will be provided.

5.4. Pharmacokinetic Assessments

Blood samples for the PK assessment of GLPG1205, pirfenidone and nintedanib should be collected as specified in the Schedule of Activities in section 2.5.

PK concentrations of GLPG1205, pirfenidone, and nintedanib will be described graphically. In addition, listings of all individual plasma concentration data will be created. [REDACTED]

5.5. Changes to the Planned Analyses, Not Covered by Protocol Amendments

[REDACTED]

Data after lung transplant will be excluded from all efficacy analyses.

[REDACTED]

In addition to descriptive statistics, ANCOVA models were included for the analysis of 6MWT distance, SGRQ score [REDACTED]

If changes are needed after unblinding these will be documented in the CSR with an explanation for the reason for the change.

APPENDIX

APPENDIX I: LABORATORY: TOXICITY GRADING

Implementation of Common Terminology Criteria for Adverse Events (CTCAE), v5.0: November 27, 2017.

Notes:

- Laboratory results for which the fasting status is missing will be considered as taken non-fasted.
- Analysis results scoring below the lowest grade limits (< grade 1) are defined as grade 0.

Table 8 Laboratory Toxicity Grades based on CTCAE v5.0

Tests	Thresholds (Conventional Units)	Thresholds (SI Units)	Grade
Hematology			
Hemoglobin decreased	<LLN - 10 g/dL	<LLN - 100 g/L	G1
	<10 - 8 g/dL	<100 - 80 g/L	G2
	<8 g/dL	<80 g/L	G3
Hemoglobin increased	>ULN - ULN + 2 g/dL	>ULN - ULN + 20 g/L	G1
	>ULN + 2 - ULN + 4 g/dL	>ULN + 20 - ULN + 40 g/L	G2
	>ULN + 4 g/dL	>ULN + 40 g/L	G3
White blood cell (WBC) count decreased	<LLN - 3000 /mm ³	<LLN - 3.0 * 10 ⁹ /L	G1
	<3000 - 2000 /mm ³	<3.0 - 2.0 * 10 ⁹ /L	G2
	<2000 - 1000 /mm ³	<2.0 - 1.0 * 10 ⁹ /L	G3
	<1000 /mm ³	<1.0 * 10 ⁹ /L	G4
WBC count increased	>100000 /mm ³	>100.0 * 10 ⁹ /L	G3
Neutrophils decreased	<LLN - 1500 /mm ³	<LLN - 1.5 * 10 ⁹ /L	G1
	<1500 - 1000 /mm ³	<1.5 - 1.0 * 10 ⁹ /L	G2
	<1000 - 500 /mm ³	<1.0 - 0.5 * 10 ⁹ /L	G3
	<500 /mm ³	<0.5 * 10 ⁹ /L	G4
Lymphocytes decreased	<LLN - 800 /mm ³	<LLN - 0.800 * 10 ⁹ /L	G1
	<800 - 500 /mm ³	<0.8 - 0.5 * 10 ⁹ /L	G2
	<500 - 200 /mm ³	<0.5 - 0.2 * 10 ⁹ /L	G3
	<200 /mm ³	<0.2 * 10 ⁹ /L	G4
Lymphocytes increased	>4000 /mm ³	>4.0 * 10 ⁹ /L	G2
	>20000 /mm ³	>20.0 * 10 ⁹ /L	G3
Eosinophiles absolute count	>ULN	>ULN	G1
Platelets decreased	<LLN - 75000 /mm ³	<LLN - 75.0 * 10 ⁹ /L	G1
	<75000 - 50000 /mm ³	<75.0 - 50.0 * 10 ⁹ /L	G2
	<50000 - 25000 /mm ³	<50.0 - 25.0 * 10 ⁹ /L	G3
	<25000 /mm ³	<25.0 * 10 ⁹ /L	G4
Coagulation			
Activated partial thromboplastin time (aPTT)	>ULN - 1.5 x ULN	>ULN - 1.5 x ULN	G1
	>1.5 - 2.5 x ULN	>1.5 - 2.5 x ULN	G2
	>2.5 x ULN	>2.5 x ULN	G3
INR (international normalized ratio) increased	>1.2 - 1.5	>1.2 - 1.5	G1
	>1.5 - 2.5	>1.5 - 2.5	G2

	>2.5		>2.5		G3
Chemistry					
Random glucose decreased (fasting)	<LLN - 55	mg/dl	<LLN - 3.0	mmol/L	G1
	<55 - 40	mg/dl	<3.0 - 2.2	mmol/L	G2
	<40 - 30	mg/dl	<2.2 - 1.7	mmol/L	G3
	<30	mg/dl	<1.7	mmol/L	G4
Creatinine increased	>ULN - 1.5 x ULN		>ULN - 1.5 x ULN		G1
	>1.5 - 3x ULN		>1.5 - 3 x ULN		G2
	> 3 - 6 x ULN		> 3 - 6 x ULN		G3
	>6 x ULN		>6 x ULN		G4
eGFR (estimated glomerular filtration rate)/creatinine clearance ml/min/1.73 m ²	<LLN - 60	ml/min	<LLN - 60	ml/min	G1
	<60 - 30	ml/min	<60 - 30	ml/min	G2
	<30 - 15	ml/min	<30 - 15	ml/min	G3
	<15	ml/min	<15	ml/min	G4
Sodium decreased	<LLN - 130	mmol/L	<LLN - 130	mmol/L	G1
	<130 - 125	mmol/L	<130 - 125	mmol/L	G2
	<125 - 120	mmol/L	<125 - 120	mmol/L	G3
	<120	mmol/L	<120	mmol/L	G4
Sodium increased	>ULN - 150	mmol/L	>ULN - 150	mmol/L	G1
	>150 - 155	mmol/L	>150 - 155	mmol/L	G2
	>155 - 160	mmol/L	>155 - 160	mmol/L	G3
	>160	mmol/L	>160	mmol/L	G4
Potassium decreased	<LLN - 3	mmol/L	<LLN - 3	mmol/L	G1
	<3 - 2.5	mmol/L	<3 - 2.5	mmol/L	G3
	<2.5	mmol/L	<2.5	mmol/L	G4
Potassium increased	>ULN - 5.5	mmol/L	>ULN - 5.5	mmol/L	G1
	>5.5 - 6	mmol/L	>5.5 - 6	mmol/L	G2
	>6 - 7	mmol/L	>6 - 7	mmol/L	G3
	>7	mmol/L	>7	mmol/L	G4
Calcium decreased	<LLN - 8	mg/dl	<LLN - 2.0	mmol/L	G1
	<8 - 7	mg/dl	<2 - 1.75	mmol/L	G2
	<7 - 6	mg/dl	<1.75 - 1.5	mmol/L	G3
	<6	mg/dl	<1.5	mmol/L	G4

Calcium increased	>ULN - 11.5	mg/dl	>ULN - 2.9	mmol/L	G1
	>11.5 - 12.5	mg/dl	>2.9 - 3.1	mmol/L	G2
	>12.5 - 13.5	mg/dl	>3.1 - 3.4	mmol/L	G3
	>13.5	mg/dl	>3.4	mmol/L	G4
AST (asparatate aminotransferase)	>ULN - 3 x ULN		>ULN - 3 x ULN		G1
	>3 - 5 x ULN		>3 - 5 x ULN		G2
	>5 - 20 x ULN		>5 - 20 x ULN		G3
	>20 x ULN		>20 x ULN		G4
ALT (alanine aminotransferase)	>ULN - 3 x ULN		>ULN - 3 x ULN		G1
	>3 - 5 x ULN		>3 - 5 x ULN		G2
	>5 - 20 x ULN		>5 - 20 x ULN		G3
	>20 x ULN		>20 x ULN		G4
GGT (gama-glutamyl transferase)	>ULN - 2.5 x ULN		>ULN - 2.5 x ULN		G1
	>2.5 - 5 x ULN		>2.5 - 5 x ULN		G2
	>5 - 20 x ULN		>5 - 20 x ULN		G3
	>20 x ULN		>20 x ULN		G4
Total bilirubin	>ULN - 1.5 x ULN		>ULN - 1.5 x ULN		G1
	>1.5 - 3 x ULN		>1.5 - 3 x ULN		G2
	>3 - 10 x ULN		>3 - 10 x ULN		G3
	>10 x ULN		>10 x ULN		G4
Alkaline phosphatase (aP)	>ULN - 2.5 x ULN		>ULN - 2.5 x ULN		G1
	>2.5 - 5 x ULN		>2.5 - 5 x ULN		G2
	>5 - 20 x ULN		>5 - 20 x ULN		G3
	>20 x ULN		>20 x ULN		G4
Albumin	<LLN - 3	g/dL	<LLN - 30	g/L	G1
	<3 - 2	g/dL	<30 - 20	g/L	G2
	<2	g/dL	<20	g/L	G3
Triglycerides (fasting)	>ULN - 500	mg/dL	>ULN - 5.7	mmol/L	G1
	>500 - 1000	mg/dL	>5.7 - 11.4	mmol/L	G3
	>1000	mg/dL	>11.4	mmol/L	G4
Cholesterol	>ULN - 400	mg/dL	>ULN - 10.34	mmol/L	G1
	>400 - 500	mg/dL	>10.34 - 12.92	mmol/L	G3
	>500	mg/dL	>12.92	mmol/L	G4
Creatine kinase (CK)	>ULN - 2.5 x ULN		>ULN - 2.5 x ULN		G1

	>2.5 - 5 x ULN	>2.5 - 5 x ULN	G2
	>5 - 10 x ULN	>5 - 10 x ULN	G3
	>10 x ULN	>10 x ULN	G4

G=grade; LLN=lower limit of normal; ULN=upper limit of normal; NA=not applicable

APPENDIX II: ADDITIONAL DETAILS ON MIXED MODEL PRIMARY ANALYSIS

Linear Mixed Model

As a sensitivity analysis for the primary analysis, the rate of decline in FVC over 6 months will be analyzed using a random coefficient regression model including sex, and stratum as categorical fixed effects and age, and height as continuous fixed effects and a random intercept and slope. The treatment effect will be determined by using estimated slopes for each study group on the basis of the time-by-treatment interaction term from the mixed model. Only post-baseline FVC values at planned time points, as specified in Section 2.5 and 3.3.3, will be used. The model will be fit using the SAS Proc Mixed procedure, details are below. The assumptions of the model will be investigated graphically.

The statistical model can be written as follows:

$$Y_{ij} = (\alpha + a_i) + (\theta + (\beta_T \theta) * Trt_i + g_i) * t_{ij} + \beta_S * Sex_i + \beta_A * Age_i + \beta_H * Height_i + \beta_{SOC} * (Standard\ of\ care)_i + \varepsilon_{ij}$$

Where

- Y_{ij} is the FVC value for subject i at time t_{ij} ,
- α and θ are the fixed effects for the intercept and slope, respectively,
- a_i and g_i are random effects for the intercept and slope for subject i , with $\mathbf{b}_i = (a_i, g_i)$ assumed to be independent and identically normally distributed with mean 0 and unstructured variance-covariance matrix for all i ,
- $(\beta_T \theta)$ is the effect of GLPG1205 on the slope,
- $\beta_S, \beta_A, \beta_{SOC}$ and β_H are subject specific demographic coefficients for sex, age, stratification factor (SOC; 2 levels) and height at baseline,
- $Trt_i = 0$ for placebo and $Trt_i = 1$ for GLPG1205, $(Standard\ of\ care)_i = 0$ for neither and $(Standard\ of\ care)_i = 1$ for pirfenidone or nintedanib,
- ε_{ij} is the random error for subject i at time t_{ij} , assumed to be independent and identically normally distributed with mean 0 and variance σ_ε^2 for all i, j .

If this model fails to converge, other structures will be tested for the variance-covariance matrix for the error terms (e.g. heterogeneous Toeplitz). Depending on the structure used, the random slope and random intercept may need to be dropped from the model. The structure with the best fit, based on Akaike's information criterion, will then be used.

The linearity assumption of the model will be explored graphically by the line plots over time of the observed FVC values (mL) as well as change from baseline and LS means at each time point.

The following SAS code is to be used:

```
proc SORT data = FVC;
  BY subject visit;
run;
proc MIXED data = FVC order = internal;
  CLASS subject treatment visit sex stratum;
  MODEL FVC = treatment * time sex age height stratum / solution CL ddfm=KR;
  RANDOM intercept time / type=UN subject = subject;
  REPEATED visit / type= Simple subject = subject;
  ESTIMATE 'GLPG1205 – Placebo' treatment*time -1 1 / e CL;
run;
```

Repeated Measures Analysis

As a sensitivity analysis for the primary analysis, the change from baseline in FVC over 26 weeks will also be compared between treatment groups by MMRM including sex, stratum, and a treatment-by-time point interaction as categorical fixed effects, age, height, and baseline FVC as continuous fixed effects and correlated within-subject residuals. Only post-baseline FVC values at planned time points, as specified in Section 2.5 and 3.3.3, will be used. The model will be fit using the SAS Proc Mixed procedure, details are below.

The statistical model can be written as follows:

$$Y_{ij} = \alpha + (\theta_j + (\beta_T \theta)_j * Trt_i) + \beta_S * Sex_i + \beta_A * Age_i + \beta_H * Height_i + \beta_{SOC} * (Standard\ of\ care)_i + \beta_B * Baseline_i + \epsilon_{ij}$$

Where

- Y_{ij} is the FVC change from baseline for subject i at time point j (excluding baseline),
- α is the intercept and θ_j is the placebo time effect at time point j ,
- $(\beta_T \theta)_j$ is the effect of GLPG1205 at time point j ,
- β_S , β_A , β_{SOC} and β_H are subject specific demographic coefficients for sex, age, stratification factor (SOC; 2 levels) and height at baseline,

■ [REDACTED]

■ [REDACTED]

■ [REDACTED]

■ [REDACTED]

[REDACTED]

[REDACTED]

[REDACTED]

[REDACTED]

[REDACTED]

[REDACTED]

[REDACTED]

[REDACTED]

[REDACTED]

■ [REDACTED]

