2.3. CLINICAL STUDY RATIONALE

IPF is a chronic and progressive lethal lung disease for which two oral treatments (pirfenidone and nintedanib) are approved in the EU and US. These treatments appear to slow disease progression however, the residual decline of FVC over one year remains substantial, with a further decline of FVC over 52 weeks of 125 mL and 114 mL in INPULSIS I and II (nintedanib) [16], respectively, and around 200 mL in the ASCEND study (pirfenidone) [15].

In addition, both compounds are frequently associated with side effects potentially limiting the use in clinical practice.

There thus remains a significant unmet medical need for the development of additional therapies targeting different disease pathways that could potentially prove to be more effective by further preventing the decline in FVC with an acceptable safety profile [22].

Recent published data suggest the relevance of GPR84 in fibrotic pathways underlined by GPR84 knock out mice used in models of kidney fibrosis [20]. In addition, PBI-4050 a compound in clinical development targeting both GPR84 and GPR40, has demonstrated first clinical benefit after 12 weeks of treatment in patients with IPF with and without addition of nintedanib [21]. It thus can be anticipated that compounds targeting GPR84 could lead to a new class of therapy for IPF.

GLPG1205 is a novel, selective, and potent GPR84 antagonist that has a good safety and tolerability profile at the targeted dose of 100 mg q.d. in clinical studies.

Consequently, it seems appropriate to investigate the efficacy, safety, tolerability and PK of GLPG1205 in subjects with IPF.

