7.3.4.1. Primary Efficacy Endpoint Analysis

The change from baseline in FVC at 26 weeks will be analyzed using an analysis of covariance (ANCOVA) model including treatment, sex and stratum as categorical covariates

and age, height and baseline FVC value as continuous covariates. Subgroup analysis may be performed for background treatment.

As a sensitivity analysis, a random coefficient regression model (random slopes and intercepts) including treatment, sex and stratum as categorical fixed effects and time, age and height as continuous fixed effects, will be used to analyze the rate of decline in FVC. The treatment effect will be determined by using estimated slopes for each study group on the basis of the time-by-treatment interaction term from the mixed model. All available FVC values from baseline to Week 26 will be used including FVC measurements at the follow-up visit for subjects who discontinue the study medication prematurely and do not complete the study visits through Week 26.

Furthermore, sensitivity analyses including multiple imputation methods may be performed using all randomized subjects to assess the impact of missing data on the primary efficacy analysis.

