5.2.2.1. Primary Endpoint: Change from Baseline in FVC over 26 Weeks

The change from baseline in FVC over 26 weeks will be compared between treatment groups by means of an analysis of covariance (ANCOVA) model at each planned time point (as specified in Section 2.5 and 3.3.3) including treatment, sex, and stratum as categorical covariates and age, height, and baseline FVC value as continuous covariates. LS means and 95% CIs will be presented per time point and treatment group as well as the LS mean differences between treatment groups with 95% CI.

Missing data will not be imputed and thus this analysis is conducted on OC only.

Percent predicted FVC will be analyzed using a similar ANCOVA model.

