5.2.2.2.1. Linear Mixed Model

A random coefficient regression model including sex, and stratum as categorical fixed effects and age, and height as continuous fixed effects and a random intercept and slope will be used to analyze the yearly rate of decline in FVC. The treatment effect will be determined by using estimated slopes for each study group on the basis of the time-by-treatment interaction term from the mixed model. The model will be fit using the SAS Proc Mixed procedure, details are in Appendix II. The assumptions of the model will be investigated graphically.

This approach provides another estimate for the primary endpoint. In addition, this model implicitly takes into account missing data under the assumption of missing-at-random (MAR).

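### SAP Appendix II fits the random-slope FVC sensitivity model to post-baseline values only, against Protocol 7.3.4.1, so baseline FVC is not used; with data to Week 26 the slope difference loses some precision

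*SAP*

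**What the plan says.** Protocol 7.3.4.1 describes a random-intercept, random-slope model as a sensitivity analysis for the primary endpoint and fixes its data: "All available FVC values from baseline to Week 26 will be used including FVC measurements at the follow-up visit for subjects who discontinue" study drug early and do not complete the visits through Week 26.

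SAP 5.2.2.2.1 carries the model forward ("A random coefficient regression model including sex, and stratum as categorical fixed effects and age, and height as continuous fixed effects") and states no limit on the data. SAP Appendix II, Linear Mixed Model, adds one: "Only post-baseline FVC values at planned time points, as specified in Section 2.5 and 3.3.3, will be used". The outcome there is the FVC value itself, and the code reads "MODEL FVC = treatment * time sex age height stratum / solution CL ddfm=KR". It contains neither a baseline FVC term nor a treatment main effect.

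The same limiting sentence appears in Appendix II for the MMRM, whose outcome is change from baseline and which has baseline FVC as a covariate.

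**The concern.** The two data rules cannot both be followed. In the MMRM the restriction is normal practice, because baseline enters through the outcome and the covariate. In the slope model it enters through neither. Both arms share one intercept at time 0, which randomization justifies, but without a time-0 observation that intercept is extrapolated back from Week 4.

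At stake is the precision of the one sensitivity analysis of the primary endpoint to which the protocol commits; its multiple imputation is only optional. The cross-reference to SAP 2.5 and 3.3.3 adds an ambiguity. Spirometry is scheduled at Week 30 and Table 2 has a Week 30 window, so two programmers could build different datasets from the same sentence.

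**Working it through.** **Inputs from the documents.** Protocol 7.1: 40 and 20 evaluable subjects, 10% dropout (hence 36 and 18), SD of the Week 26 change 200 mL, true differences 50 and 80 mL in a 50:50 mix (mean 65 mL). SAP 2.5: spirometry at Weeks 0, 4, 8, 12, 16, 20, 26 and 30.

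**The plan's own figures.** SE = 200 × √(1/36 + 1/18) = 57.7 mL. Φ((65 − 40)/57.7) = 66.7% and Φ((65 − 20)/57.7) = 78.2%, matching the stated 67% and 78%. The documents give no precision figure for the slope model.

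**Spread of the time points.** The within-subject sum of squares of time is 1556 − 86²/7 = 499.4 weeks² for Weeks 0 to 26, and 1556 − 86²/6 = 323.3 weeks² for Weeks 4 to 26. That is a fall of 35%. If subjects did not differ in true slope, the SE ratio would be about √(499.4/323.3) = 1.24. Slope variation dilutes this.

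**Standard error of treatment × time.** Generalized least squares: Var = (Σ n_g X_g′V⁻¹X_g)⁻¹, with V = ZDZ′ + σ²I and X = (1, time, treatment × time), as in the SAP code. Assumed, because the documents do not give them: intercept SD 300, 500 or 700 mL; intercept-slope correlation −0.3, 0 or 0.3. Residual SD σ and slope SD s (mL/year) are tied to the protocol's 200 mL by (0.5s)² + 2σ² = 200². For example, s = 200 gives 100² + 2σ² = 40,000, so σ = 122 mL.

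SEs are in mL per 26 weeks at intercept SD 500 and correlation 0. Ratios are relative to the protocol data (Weeks 0–26) and cover all assumed intercept SDs and correlations.

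| Residual SD | Slope SD | SE, Weeks 0–26 | SE, Weeks 4–26 | Ratio, Weeks 4–26 | Ratio, Weeks 4–30 |
|---|---|---|---|---|---|
| 50 | 374 | 56.5 | 57.9 | 1.02–1.03 | 0.995–0.999 |
| 80 | 330 | 54.6 | 58.0 | 1.05–1.07 | 0.985–0.996 |
| 94 | 300 | 53.4 | 58.0 | 1.07–1.10 | 0.979–0.992 |
| 100 | 283 | 52.7 | 58.0 | 1.08–1.11 | 0.975–0.990 |
| 122 | 200 | 50.0 | 57.9 | 1.14–1.17 | 0.958–0.980 |
| 137 | 100 | 47.7 | 57.7 | 1.18–1.22 | 0.946–0.970 |

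Adding a treatment main effect, which the protocol's list of fixed effects includes, moved the Weeks 4–26 ratio by less than 0.02 (residual SD 60 to 120 mL, intercept SD 400 or 600 mL). If the time-0 value is the mean of two pre-dose values, in line with the SAP 3.3.3 definition of the spirometry baseline, the loss over that same range is 4 to 26%, against 3 to 17% with a single value.

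**Does the rule bias the estimate?** The expected slope difference × 0.5 year was computed over residual SD 94 to 137 mL. Protocol 2.3 reports "a further decline of FVC over 52 weeks of 125 mL and 114 mL" on nintedanib and around 200 mL on pirfenidone.

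| Benefit profile | Week 26 benefit | Weeks 0–26 | Weeks 4–26 |
|---|---|---|---|
| Linear | 65 | 65 | 65 |
| 114 mL/year decline halted | 57 | 57 | 57 |
| 125 mL/year decline halted | 62.5 | 62.5 | 62.5 |
| 200 mL/year decline halted until 65 mL gained | 65 | 69.6–71.7 | 61.1–65.2 |
| 300 mL/year, same (rate assumed) | 65 | 62.4–67.3 | 43.0–52.3 |
| 400 mL/year, same (rate assumed) | 65 | 55.1–61.9 | 28.2–41.0 |
| Full 65 mL gap by Week 4 | 65 | 38.5–48.9 | −3.1 to 16.7 |

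The last row needs FVC to rise. Halting a decline of 114 to 200 mL/year gains only 114 × 4/52 = 8.8 mL to 200 × 4/52 = 15.4 mL in four weeks.

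**The case against.** The best reply is that little depends on this. It is one sensitivity model in a proof-of-concept study without a formal sample size calculation. The primary ANCOVA and the MMRM both adjust for baseline FVC, and the MMRM gives a second analysis valid under missing at random. That stands, and it limits the weight of the point.

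The size of the loss also rests on assumed variances. At residual SD 50 to 80 mL it is only about 2 to 7%. That stands too. The direction does not depend on the variances: for data to Week 26, dropping a valid observation from a correctly specified fit cannot improve precision.

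A literal reading of the cross-reference admits Week 30, and the SE then falls by about 1 to 5% relative to the protocol data at residual SD 94 to 137 mL, and by less at smaller residual SDs. So precision is not lost on every reading. The gain, however, comes from completers' off-drug values, whereas the protocol adds follow-up FVC only for early discontinuers. Appendix II itself describes "the rate of decline in FVC over 6 months will be analyzed using a random coefficient regression model", which points to Week 26.

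A reader might infer that the rule would hide an early benefit. The documents do not support that. At the decline rates in Protocol 2.3 both rules are unbiased or, at 200 mL/year, the SAP rule is no further from 65 mL than the protocol rule. Clear understatement needs steeper decline than the documents report, or a rise in FVC. The plan would also help to reveal an early plateau: "The linearity assumption of the model will be explored graphically by the line plots over time of the observed FVC values (mL"), and for the primary ANCOVA "LS means and 95% CIs will be presented per time point and treatment group as well as the LS mean differences between treatment groups".

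A reader might also call the change undeclared. The visible text of SAP 5.5 does not list it, but that section is partly redacted, so this cannot be judged.

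**Conclusion.** The contradiction is certain on the text: the slope model as written in Appendix II makes no use of baseline FVC, while the protocol includes it. With data to Week 26 the SE of the slope difference rises in every scenario examined, by about 2 to 22%. This rests on 36 and 18 subjects, a single time-0 value, the protocol's 200 mL SD and assumed variance components. If Week 30 is admitted there is no precision loss, but the dataset then departs from the protocol in a second way.

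The point does not extend to bias at the documented decline rates, or to the primary ANCOVA or the MMRM. It should be corrected because the two documents prescribe different data for a committed analysis and the correction is nearly free.

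**What to change.** For the slope model only, replace the sentence in Appendix II with wording such as: *The slope model uses every available FVC value from baseline (time 0) through Week 26; follow-up FVC is added only for subjects who discontinued IMP early and did not complete visits through Week 26.* State which pre-dose value stands at time 0: the SAP 3.3.3 mean or the Visit 2 value. Keep the existing sentence for the MMRM. If a post-baseline-only slope model is intended, declare it in SAP 5.5 with a reason and say whether Week 30 counts.

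The cost is a few lines of SAP text and one data-selection rule, settled before unblinding. How Visit 9 values delayed by COVID-19 enter the mixed models is a separate question and not part of this change.
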